- Absence of chronic kidney disease
- ECOG 0-1.
- Absence of encephalopathy.
- Informed consent.

Contraindications

- Advanced liver disease.
- Thrombosis or reversal of portal flow.
- Vascular invasion.
- Extrahepatic spread.
- Contraindication to administration of cytostatics.
- Contraindication to angiographic procedure.

HYPOTHESIS:

The use of 100 micron-TANDEM[®] spheres will be studied with the synergistic effect of being administered through SEQUIRE[®] microcatheter anti-reflux protection system, which may allow the administration of the maximum doses of doxorubicin, avoiding the undesired occlusion of collateral arterial segments (SYNERGIC EFFECT). Other variables to study are: access route, procedural time and fluoroscopy time.

The information will be collected through the electronic database of the patient (includes laboratory data). Patients will be evaluated starting from the date of inclusion as candidates for TACE treatment, and followed up for 6 months (unless patients are lost to clinical follow-up or death occurs). Mortality data are obtainable by searching the electronic history of the patient.

Changes in the serum levels of aspartate aminotransferase (AST), alanine aminotransferase (ALT), Alkaline phosphatase (ALP), bilirubin, albumin and patients' complete hematological profile, as well as serum lipase and amylase levels within the 1st week post-TACE to detect pancreatitis, will be evaluated at the following time-points: pre-embolization, at one month, three months, and six months. Computed tomography (CT) or Magnetic Resonance Imaging (MRI) with contrast will be performed at the same time-points as just indicated; modified Response Evaluation Criteria in Solid Tumors (m-RECIST) will be used, and images will be assessed by two experienced radiologists (any discordant interpretation will be solved through team consensus). All serologic toxicities would be classified according to common terminology criteria for adverse effects. On this scale, severe hepato-toxicity (grade 3) is classified as the increase of up to 5 times the normal limit of AST, ALT, FA or the increase of bilirubin level to over 3 g/dl.

PATIENT SELECTION:

Between October 2020 and December 2021, and expected number of 30 patients will be treated. The diagnosis of Hepatocellular carcinoma (HCC) will confirm in accordance with the American Association for the Study of Liver Diseases guidelines and HCC staged according to Barcelona Clinic Liver Cancer (BCLC) system.

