DEB-TACE is indicated according to clinical practice guidelines referred above.

TECHNICAL PROCEDURE:

The embolization will be performed using TANDEM[®] spheres (each cc of spheres can be loaded with up to 50 mg of doxorubicin. The maximum dose of doxorubicin used per procedure was 150 mg, corresponding to 3 cc of spheres) and SEQUIRE[®] microcatheter in a super-selective tumour's arterial position avoiding undesired arterial branches. The procedure will consider super-selective when the micro-catheter tip reached the tumour feeding artery. Each cc of microspheres will mix with 7-10 cc of non-ionic contrast medium. Embolization endpoint is considered vascular stasis or 150 mg of Doxorubin administered.

OBJECTIVES AND END-POINTS:

Efficacy:

[figure not shown]
- Technical success will be defined as a composite outcome measurement: ability to place the microcatheter inside the required vascular segment and qualitative assessment of microspheres deposition in the target tumour.

- Time to Progression (TTP) [Time Frame: 6 months]. Time at which progression is first observed in a tumor assessment according to mRECIST as assessed by CT or MRI.
- Objective Response Rate (ORR) and Disease Control Rate (DCR) [Time Frame: Assessed at 1, 3, and 6 months after first treatment]. ORR is defined as a complete or partial response among the total number of cases and DCR is defined as a complete, partial response or stable disease among the total number of cases, according to mRECIST evaluated by CT or MRI. Time to retreatment included as consequential secondary objective.

Safety:

- Adverse Events (AEs) and Serious Adverse Events (SAE) [Time Frame: Assessed at 1, 3, and 6 months after first treatment. The incidence of emerging AE and SAE will be summarized according to standardized qualification criteria [Journal of Vascular Interventional Radiology (JVIR) SAE], including pancreatitis, cholecystitis, clinical presentations, postembolization syndrome (PES), etc.
- Non Target embolization (NTE) by thorough angiographic assessment of the whole liver vasculature after TACE, as well as Cone Beam Computed Tomography (CBCT) **performed immediately following embolization (within 30 minutes from the end of procedure) to evaluate off-target distribution.**
- Health-Related Quality of Life questionnaire (HRQOL): pre-treatment and post-treatment quality of life assessment using the specific questionnaire for functional assessment for cancer treatment (FACT-G).

Study flowchart

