SECONDARY OBJECTIVES:
1-TTP
2-HRQOL
3-Time to retreatment

DEB-TACE PROCEDURES:

The embolization will be performed according to routine clinical practice, with drug-eluting microspheres (100-micron TANDEM[®] spheres), pre-loaded with 50 mg doxorubicin per ml (1 syringes of 3 ml). Injection will be according to manufacturer recommendations, with a selective or superselective approach depending on lesion and feeder localization.

RECIST	mRECIST for HCC
CR = Disappearance of all target lesions	CR = Disappearance of any intratumoral arterial enhancement in all target lesions
PR = At least a 30% decrease in the sum of diameters of target lesions, taking as reference the baseline sum of the diameters of target lesions	PR = At least a 30% decrease in the sum of diameters of viable (enhancement in the arterial phase) target lesions, taking as reference the baseline sum of the diameters of target lesions
SD = Any cases that do not qualify for either partial response or progressive disease	SD = Any cases that do not qualify for either partial response or progressive disease
PD = An increase of at least 20% in the sum of the diameters of target lesions, taking as reference the smallest sum of the diameters of target lesions recorded since treatment started	PD = An increase of at least 20% in the sum of the diameters of viable (enhancing) target lesions, taking as reference the smallest sum of the diameters of viable (enhancing) target lesions recorded since treatment started

AASLD, American Association for the Study of Liver Diseases; JNCI, Journal of the National Cancer Institute; HCC, hepatocellular carcinoma; mRECIST, modified Response Evaluation Criteria in Solid Tumors; CR, complete response; PR, partial response; SD, stable disease; PD, progressive disease.

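### Does the missing word 'viable' in the partial-response reference of the mRECIST table put the objective response rate at risk?

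*Protocol*

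**What the plan says.** The table under DEB-TACE PROCEDURES sets RECIST beside mRECIST.

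- RECIST, partial response (PR), reads: "At least a 30% decrease in the sum of diameters of target lesions, taking as reference the baseline sum of the diameters of target lesions".
- mRECIST, PR: a fall of at least 30% in the diameters of "viable (enhancement in the arterial phase) target lesions, taking as reference the baseline sum of the diameters of target lesions".
- mRECIST, complete response (CR): "Disappearance of any intratumoral arterial enhancement in all target lesions".
- mRECIST, progressive disease (PD): a rise of at least 20% in the viable sum, "taking as reference the smallest sum of the diameters of viable (enhancing) target lesions recorded since treatment started".

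Stable disease (SD) is the remainder and has no reference of its own. In the mRECIST column, then, only PR and PD name a reference sum. PD names a viable sum; PR repeats the RECIST reference.

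Under OBJECTIVES AND END-POINTS, Efficacy, "ORR is defined as a complete or partial response among the total number of cases", judged by mRECIST at 1, 3 and 6 months. Time to progression (TTP) is the "Time at which progression is first observed in a tumor assessment according to mRECIST". Under HYPOTHESIS, two radiologists with experience read the images, and "any discordant interpretation will be solved through team consensus". Under PATIENT SELECTION, an "expected number of 30 patients will be treated".

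**The concern.** The PR row appears to measure one thing and compare it with another: enhancing diameter at follow-up against whole-lesion diameter at baseline. If a lesion already has a non-enhancing part before treatment, that part would count towards the 30% fall although treatment did nothing to it. Some patients with SD would then be recorded as PR.

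PR feeds ORR directly. The study describes no comparator, so ORR would be read as an absolute figure and set beside other series that may have used a viable baseline. Consensus reading settles disagreements between readers but does not say which baseline sum to use. Disease control rate and TTP are not at stake, because exchanging SD for PR changes neither.

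A second worry is that PR refers to baseline and PD to the smallest sum so far, so that one scan may meet both rows.

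**Working it through.** The protocol gives no ORR assumption, threshold or sample-size derivation, so there is no figure of its own to reproduce. The check is threshold algebra.

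**Inputs**
- PR threshold 30% and PD threshold 20%: the mRECIST table.
- Expected number of patients 30: PATIENT SELECTION.
- Viable share at baseline, f = V0/T0, where V0 is the viable sum and T0 the whole-lesion sum: not given. Assumed range 0.60 to 1.00.
- V1 is the viable sum at follow-up.

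**Three readings of the PR row**
1. Same quantity, viable against viable: V1 ≤ 0.70 × V0. The viable fall needed is 30% for every f.
2. Mixed, follow-up viable against baseline whole lesion: V1 ≤ 0.70 × T0. The viable fall needed is 1 − 0.70/f.
3. Viable decrease as a share of the baseline whole lesion: (V0 − V1)/T0 ≥ 0.30. The viable fall needed is 0.30/f.

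| f | Reading 1 | Reading 2 | Reading 3 |
|---|---|---|---|
| 1.00 | 30% | 30% | 30% |
| 0.95 | 30% | 26.3% | 31.6% |
| 0.90 | 30% | 22.2% | 33.3% |
| 0.80 | 30% | 12.5% | 37.5% |
| 0.70 | 30% | 0% | 42.9% |
| 0.60 | 30% | −16.7% | 50% |

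**One patient**, with assumed T0 = 5.0 cm, V0 = 4.0 cm (f = 0.80) and V1 = 3.4 cm:
- Reading 1: (4.0 − 3.4)/4.0 = 15%, so SD. The PR cut-off is 0.70 × 4.0 = 2.8 cm.
- Reading 2: (5.0 − 3.4)/5.0 = 32%, so PR. The cut-off is 0.70 × 5.0 = 3.5 cm.
- Reading 3: (4.0 − 3.4)/5.0 = 12%, so SD. The cut-off is 4.0 − 0.30 × 5.0 = 2.5 cm.

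**Which reading fits the text?** The row asks for a decrease in the viable sum. Reading 2 breaks that requirement: at f = 0.70 it grants PR with no decrease, and at f = 0.60 it accepts a 16.7% increase. Reading 3 honours both the decrease and the stated denominator, and it raises the bar. Reading 1 takes the baseline value of the quantity being measured and matches the PD row. So the claim that a literal reading must inflate ORR is not established.

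**Effect on ORR.** One patient in 30 is 1/30 = 3.3 points. For illustration only, assume viable falls distributed Normal with mean 40% and SD 35%, capped at 100%:
- All lesions fully enhancing: 61.3% on every reading.
- One patient in five at f = 0.80: 61.3%, 64.7% and 59.6% on readings 1, 2 and 3. Relative to reading 1 that is +3.4 and −1.7 points, or about +1.0 and −0.5 patients in 30.
- Every patient at f = 0.80: 61.3%, 78.4% and 52.8%.

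The last line is an extreme case that shows what would have to be true for the reading to matter much.

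**PR and PD on one scan.** A fully enhancing 6.0 cm at baseline, 3.0 cm at 1 month and 4.0 cm at 3 months is (6.0 − 4.0)/6.0 = 33% below baseline and (4.0 − 3.0)/3.0 = 33% above the smallest sum. The overlap is real, but the plain RECIST column has the same baseline-and-nadir structure. It does not come from the missing word, and the order of precedence is commonly left to the analysis plan.

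**The case for a change.** The best case for a change is that this table is the protocol's only operational definition of PR. The table uses the viable qualifier where it means enhancing tissue and omits it where it means the whole lesion, so on its own vocabulary the PR reference is the whole lesion. No other section corrects it. The eligibility criteria do not require lesions to be untreated or fully enhancing, so f below 1 is not excluded. Two readers could measure identically and still classify a patient differently. The correction would cost a few words.

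Much of this stands: the row is inconsistent with the PD row, and nothing in the text settles it. Three things weaken it. The contrast is one row against one other, since CR and SD carry no reference. Readers who apply mRECIST to the viable sum at each visit have little reason to switch to whole-lesion diameter for one baseline figure. And the low cost of a correction does not show that the plan would otherwise produce a wrong result.

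**Conclusion.** No change follows. The qualifier is missing from the PR reference, and where lesions are partly non-enhancing at baseline the row has more than one reading. But the direction is not fixed: at a viable share of 80% the required fall is 12.5%, 30% or 37.5%. The reading that would inflate ORR conflicts with the row's own demand that the viable sum decrease. The ordinary reading, viable against viable, is coherent and agrees with the PD row.

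The size is 3.3 points of ORR per reclassified patient if 30 are treated. The number reclassified cannot be derived from the protocol and is zero if all target lesions enhance fully. No stated ORR threshold, comparison or power figure depends on the row, and ORR is not in the list headed SECONDARY OBJECTIVES, which names TTP, quality of life and time to retreatment.

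The conclusion assumes that the radiologists will use the same viable measurement at baseline and follow-up, as the mRECIST heading and the PD row imply. It would weaken only if many patients had substantial non-enhancing tumour at baseline and whole-lesion diameters were in fact used as the reference.
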